Based on the currently available nonclinical as well as clinical safety data, there is no objection against administration of single doses of tepotinib to healthy subjects. It is recognized that healthy subjects will not get benefit by participating in this study. However, this study will generate mandatory human data about the potential of drug-drug interaction (DDI) of a proton pump inhibitor (omeprazole) on the PK of tepotinib, which is of importance in the context of concomitant medication in tumor patients with hepatic impairment treated with tepotinib. This is basic information to safeguard the further clinical development of tepotinib in patients suffering from malignancies such as HCC. During the development of tepotinib, in all 3 studies performed in healthy subjects (n = 79), the subjects well tolerated a single or 3 doses of tepotinib (different dose levels up to 500 mg single dose). All treatment emergent adverse events (TEAEs) were mild to moderate, except one Grade 3 asymptomatic lipase elevation in 1 subject. TEAEs did not show a pattern across all 3 trials. No serious adverse events (SAEs) were reported and no subject died. No clinically significant findings regarding laboratory parameters, vital signs and ECG including corrected QT interval according to Fridericia (QTcF) values were noted.

Elevations in serum lipase and amylase are considered as identified risks for subjects administered tepotinib. These elevations were observed in 5 of 79 healthy subjects exposed to tepotinib and were mild to moderate in severity (exception: one Grade 3 lipase elevation) and without apparent dose dependency. All increases of serum amylase/lipase were asymptomatic and not associated with a pancreatitis.

Subjects enrolled in this study might be exposed to a risk, including pancreatic enzyme elevation. However, inclusion of healthy subjects is justified when the administration of tepotinib is limited to a single dose or short term multiple administrations that will be given under close monitoring conditions to reduce the risk for untoward effects.

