5.5.2 Withdrawal from the Trial

Subjects must be withdrawn from the study by the Investigator at any time for any of the following reasons:

- Subject withdrew consent
- Subject lost to Follow-up

- Participation in another clinical study
- Relevant adverse events (AEs), especially serious adverse events (SAEs), occur that do not justify the subject's continuation in the study
- Pregnancy
- Protocol noncompliance judged as significant by the Investigator and/or Sponsor
- Use of a non-permitted concomitant drug as defined in Section 6.5. However, any medications that are considered necessary for the subject's wellbeing (eg paracetamol up to 1500 mg per day) may be given at the discretion of the Investigator
- Subject is no longer able to participate for other medical reasons (eg surgery, intercurrent illness)
- Any other condition which to the opinion of the Investigator no longer justifies or permits a safe participation of the subject.
- Any of the following individual stopping criteria is met unless deemed unrelated to study drug(s) (IMPs) by the Investigator with alternate etiology identified:
 - Abnormal clinically relevant vital signs confirmed on 2 or more measurements (min. 5 minute intervals), including abnormal blood pressure
 - o hypotension defined as systolic < 80 mmHg and/or diastolic < 40 mmHg, or
 - o hypertension defined as systolic > 160 mmHg and/or diastolic > 100 mmHg
 - Abnormal clinically relevant ECG findings, including a corrected QT-interval (ad modus Fridericia; QTcF) > 500 ms or an increase in QTcF > 60 ms compared to baseline, confirmed on ≥ 2 repeat measurements
 - Marked increases in liver or renal parameters (ALT/AST $\geq 3 \times$ upper limit of normal range (ULN), total bilirubin $\geq 2 \times$ ULN), creatinine $> 1.5 \times$ (ULN) confirmed by ≥ 2 repeat measurements
 - Any clinically relevant symptom or sign which in the opinion of the Investigator and/or Sponsor warrants subject withdrawal

If a subject has failed to attend scheduled trial assessments, the Investigator must determine the reasons and the circumstances as completely and accurately as possible.

In case a subject should be withdrawn from the trial, the medical monitor and clinical trial leader at the Sponsor will be informed immediately.

If there is a medical reason for the withdrawal, appropriate medical care will be provided.

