For all findings with major deviation and/or possible pathological relevance, follow-up examinations will be carried out until the deviation returns to normal or the absence of pathological relevance can be confirmed. If a deviation considered clinically relevant has not returned to a normal or not clinically relevant value when it is checked during the screening laboratory tests, the subject will not be included in the trial.

Laboratory abnormalities considered clinically relevant by the Investigator will be reported as AE. The following parameters will be determined as summarized in [Table 4](#).

The Sponsor should receive a list of laboratory normal ranges before shipment of the IMP. Any change in laboratory normal ranges during the trial should be forwarded to the Sponsor, including laboratory certificates.

For the amount of blood taken in this study see [Appendix II](#).

Table 4 Safety Laboratory Evaluations

Biochemistry	Aspartate aminotransferase Alanine aminotransferase Alkaline phosphatase γ-Glutamyl-transferase Lactate dehydrogenase Creatine phosphokinase ^a Amylase Lipase	Bilirubin (total) ^b Cholesterol Triglycerides Uric acid	Sodium Potassium Creatinine Urea Glucose
Hematology	Hematocrit Hemoglobin Red blood cell count Mean corpuscular volume Mean corpuscular hemoglobin Mean corpuscular hemoglobin concentration	Platelet count White blood cell count	White blood cell differentials and absolute counts: ^c Basophiles Eosinophils Lymphocytes Monocytes Neutrophils
Urinalysis	pH Nitrite Protein Glucose Leukocytes Blood	Ketone bodies Urobilinogen Bilirubin Urine pregnancy test, females only	Microscopic examination ^d
Urine drug screen	Cocaine Amphetamines Methamphetamines Opiates	Barbiturates Benzodiazepines Methadone Cannabinoids	Tricyclic antidepressants Cotinine Ecstasy
Other tests	Hepatitis B surface antigen Hepatitis C antibody HIV1/HIV2 antibodies Follicle stimulating hormone (if applicable) Thyroid stimulating hormone Serum pregnancy test (beta-HCG), females only eGFR ^e Alcohol breath test (at Screening and each Admission)		

HIV = human immunodeficiency virus, HCG = human chorionic gonadotropin

a In case of an increased creatine phosphokinase (CK), myocardium/brain type (CK-MB) will be determined; if the ratio of CK/CK-MB is above 6, troponin will be determined as well.

b In case of an increased Bilirubin (total) the direct Bilirubin will be determined.

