Repeated laboratory assessments will be flagged as repeats in the subject data listings and not included in summary tables statistics (unless the scheduled measurement was considered unreliable, e.g. due to technical reasons, and needed to be replaced by an unscheduled repeat measurement).

In this phase 1 PK study missing observations will be assumed to be missing completely at random (MCAR). No action will be taken to handle missing data. A subject who withdraws prior to the last planned observation in a trial period will be included in the analyses up to the time of discontinuation.

The following treatment labels will be used in listing and tables:

- tepotinib, fed
- tepotinib + omeprazole, fasted
- tepotinib + omeprazole, fed

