## **15.3 Clinical Laboratory Evaluation**

All laboratory data will be reported with SI units. Laboratory parameters will be listed by subject and time-point and summarized indicating the treatment at the respective time-point using descriptive statistics for absolute values and change from baseline over time.. Data listings of abnormalities as per the NCI-CTCAE guideline will be provided. Shift tables for laboratory tests will be presented by treatment. Shift tables will be based on NCI-CTCAE grades, where possible, and on normal ranges otherwise. They will be produced for

- End of Trial versus Screening
- Discharge versus Pre-dose (Tepotinib administration) within periods.

Laboratory values that are outside the normal range will also be flagged in the data listings, along with corresponding normal ranges and NCI-CTCAE grade and will additionally be listed separately.

See section 7.4.3 of the clinical study protocol for a table of the safety laboratory evaluations.

Safety laboratory values are separated into:

- Hematology
- Biochemistry
- Urinalysis
- Other tests

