## 15.5                    **ECG Evaluation**

ECG data will be listed by subject and time-point and summarized by absolute values and changes-from-baseline by treatment group using descriptive statistics. Descriptive statistics tables will start at baseline. Clinically significant ECG findings for individual subjects will be listed and summarized.

The time intervals [PR, QRS, RR, QT and corrected QT intervals [based on Fridericia's formula, QTcF] will be summarized descriptively by treatment.

The Fridericia's Correction (QTcF) is derived as follows:

$$\text{Fridericia's Correction (QTcF)} \quad QTc_f = \frac{QT}{\sqrt[3]{RR}}$$

where: RR = RR-interval measured in seconds.

Observed QTcF values will be categorized according to their absolute values into the categories

- $\leq 430$  ms,
- $> 430$  and  $\leq 450$  ms,
- $> 450$  and  $\leq 480$  ms,
- $> 480$  and  $\leq 500$  ms, and
- $> 500$  ms,

and categorized according to their absolute change from baseline into the categories

- $\leq 30$  ms,
- $> 30$  and  $\leq 60$  ms, and
- $> 60$  ms.

The number and percentage of subjects by these categories at any post-dose assessment will be tabulated by treatment group. All ECG measurements will be listed, with abnormalities indicated.

Investigator reported interpretation results will also be listed and tabulated treatment using the number and percentage of subjects for each interpretation category (Normal, Abnormal Not Clinically Significant [NCS], Abnormal Clinically Significant [CS].

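### No by-treatment laboratory table shows the worst post-tepotinib grade, so a Grade 1 to 2 lipase or amylase rise that peaks on a repeat sample may show its peak only in listings

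*SAP*

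**What the plan says.** **Repeats.** SAP 9 (General Specifications for Data Analyses) says "Repeated laboratory assessments will be flagged as repeats in the subject data listings and not included in summary tables statistics". The one exception reads "unless the scheduled measurement was considered unreliable, e.g. due to technical reasons, and needed to be replaced by an unscheduled repeat measurement".

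**Shift tables.** SAP 15.3 plans two, graded by NCI-CTCAE where possible: "End of Trial versus Screening" and "Discharge versus Pre-dose (Tepotinib administration) within periods". It also plans descriptive statistics over time, a listing of all values, and a separate listing of out-of-range values with their grade.

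**Sampling.** Protocol Tables 2 and 3 schedule three laboratory samples per period: Day -1, before tepotinib, and before discharge 72 h after tepotinib. Protocol 7.4.3 adds unscheduled samples: "For all findings with major deviation and/or possible pathological relevance, follow-up examinations will be carried out until the deviation returns to normal", or until the finding is shown not to matter. Protocol 5.5.2 requires at least two repeat measurements to confirm its stopping criterion that begins "Marked increases in liver or renal parameters".

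**The risk.** Protocol 3 says: "Elevations in serum lipase and amylase are considered as identified risks for subjects administered tepotinib". It reports them in 5 of 79 healthy subjects, all without symptoms, and mild to moderate apart from one Grade 3 lipase value.

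**The comparison in the same SAP.** For QTcF categories, SAP 15.5 says: "The number and percentage of subjects by these categories at any post-dose assessment will be tabulated by treatment group".

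**The concern.** The subjects who have repeat samples are those whose scheduled value already looked abnormal. A rule that drops repeats from the laboratory tables therefore removes data mainly from the subjects of interest. With one scheduled post-tepotinib sample per treatment and no worst-grade table, the by-treatment tables can report only the grade at 72 h. If the value is higher on a later sample, the tables show the lower grade.

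At stake is one part of a secondary objective: tolerability of tepotinib alone and with omeprazole. The part concerned is the laboratory finding that the protocol itself names as an identified risk. The pharmacokinetic endpoints are not affected.

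**Working it through.** **1. Scheduled samples.** One at Screening, three in each of three periods and one at End of Trial: 1 + 3 + 3 + 3 + 1 = 11. This matches the 11 biochemistry samples in Protocol Appendix II. Protocol 7.1.2 mentions Day 1 among the activities after dosing in Treatment A, but Table 2 and Appendix II count only the pre-dose sample on that day.

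**2. Scheduled post-tepotinib samples that enter a shift table.** Three discharge samples and one End of Trial sample, 3 + 1 = 4 per subject. Follow-up repeats add none. They are left out by the SAP 9 rule, and both shift tables are in any case tied to named visits.

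**3. Which shift isolates a treatment.** Discharge versus pre-dose does. End of Trial versus Screening does not: it falls 7 (±1) days after the last dose, and its reference value precedes all three treatments.

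**4. What reaches a by-treatment table when the peak is on a repeat.**

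| Rise | Laboratory tables | Adverse event tables |
|---|---|---|
| Grade 3 or higher lipase or amylase | 72 h grade only | Yes: recorded as an event of special interest (Protocol 7.4.1.4), so it should enter the TEAE tables (SAP 15.1.1) |
| Leads to discontinuation | 72 h grade only | Yes: reportable (Protocol 7.4.1.1) and summarised (SAP 15.1.2) |
| Judged clinically relevant | 72 h grade only | Yes (Protocol 7.4.3) |
| Grade 1 to 2, no symptoms, not judged relevant or medically important | 72 h grade only | No |

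Only the last row is left without a table for its peak grade. By the protocol's account of the earlier studies, Grade 1 to 2 without symptoms is also the usual presentation.

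**5. Direction.** The worst grade over a set of samples that includes discharge cannot be lower than the discharge grade. Compared with the worst grade, the discharge table can only be equal or lower.

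**6. Scale.** Assume that the earlier per-subject rate carries over.
- Rate: 5/79 = 6.3% (exact 95% confidence interval 2.1% to 14.2%).
- Expected subjects with an elevation: 12 × 5/79 = 0.76.
- Chance of at least one: 1 − (74/79)^12 = 54%, or 22% to 84% across that interval.
- Weight of one subject in a treatment column of 12: 1/12 = 8.3 percentage points.

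These figures concern any elevation. The gap also needs a higher grade on a repeat than at 72 h, and a rise that stays outside the adverse event tables. The documents give no time course for either enzyme, so that further step cannot be computed.

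**The case against.** The case against is strong on several points.

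- **The discharge table is correct as labelled.** It reports the discharge grade, and it does not contradict a listing of all abnormal values. A reader might infer that subjects are mis-graded; they are not. What is missing is a second table that answers a different question.
- **Other routes exist.** A reader might infer that only the 72 h value is ever shifted, or that values leading to withdrawal could be absent from every summary. SAP 15.3 also shifts End of Trial against Screening, and SAP 9 restricts laboratory statistics, not adverse event tables. Grade 3 or higher rises and discontinuations have their own route.
- **Listings are readable with 12 subjects.** Repeats are flagged there, and out-of-range values carry their grade. This stands, and it limits the harm. The safety objective is nevertheless reported by treatment, and a reader of the tables alone would miss the peak.
- **The QTcF rule is not a clean precedent.** ECGs have seven scheduled post-dose times per period, so they need a rule for combining them; laboratory tests have one such time. SAP 15.5 also does not say that unscheduled ECGs count. It shows that the SAP uses an any-time summary elsewhere, not that the SAP is inconsistent.
- **Excluding repeats from time-point means is sound practice.** Agreed, and the fix keeps it.

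What is left after these points is the last row of the table in the working.

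**Conclusion.** The point holds in a narrow form. As written, the SAP has no by-treatment laboratory table that shows the worst post-tepotinib grade including repeats. A symptom-free Grade 1 to 2 lipase or amylase rise that peaks on a follow-up sample, and is not judged clinically relevant or otherwise medically important, shows its peak grade only in listings. The tables can understate the worst grade but not overstate it.

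The frequency is unknown. The 54% might be read as the chance of an understated grade. It is the chance that at least one of 12 subjects has any elevation, assuming the earlier rate applies here, so it is only a ceiling at that rate. Severity is low: safety is a secondary objective in a descriptive study of 12 subjects, and the values remain visible in the listings. The point is worth making because it concerns the identified risk and costs very little to close.

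**What to change.** Keep scheduled-only values for the time-point statistics, and keep both existing shift tables.

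- **SAP 15.3:** add one by-treatment table of worst post-tepotinib NCI-CTCAE grade against pre-tepotinib grade, for lipase, amylase, ALT, AST, total bilirubin and creatinine. The last four are the parameters in the liver and renal stopping criterion, where repeats are also expected.
- **Window:** count scheduled and repeat values from tepotinib dosing until before the next period's Day -1 sample, or to the last follow-up value in Period 3. The Day -1 sample should stay out. At the minimum 14-day washout it falls 14 − 5 = 9 days after the previous tepotinib dose if B or C follows, and 14 − 1 = 13 days if A follows. When B or C follows it is also that period's baseline under SAP 9, so one value would serve as both outcome and baseline.
- **SAP 9:** add *Repeats are excluded from descriptive statistics by time point but included in worst-grade tables.*

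**Cost.** One extra table from data already collected, and a short SAP edit. Subjects with repeats have more chances to show a high grade, which is acceptable in a worst-grade safety table and can be footnoted. No clinical rule, sampling time or pharmacokinetic analysis changes.

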## **10 Trial Subjects**

### **10.1 Disposition of Subjects and Discontinuations**

This following will be presented in a summary table:

- Total number of subjects screened (ie, subjects who gave informed consent)

- Number of screened subjects who discontinued from the trial prior to treatment overall and grouped by the main reason for discontinuation:
  - Subject did not meet all eligibility criteria
  - Withdrew consent
  - Other
- Number of treated subjects
- Number and percentage of treated subjects who completed study
- Number and percentage of treated subjects who discontinued the study, with the primary reason of discontinuation:
  - Adverse event
  - Lost to follow-up
  - Protocol non-compliance
  - Death
  - Withdrew consent
  - Other
- Number and percentage of subjects who completed period (for periods 1, 2 and 3)
- Number and percentage of subjects who discontinued period and reason for discontinuation (for periods 1, 2 and 3)

A listing of discontinued subjects will be provided.

## 10.2 Protocol Deviations

### 10.2.1 Important Protocol Deviations

Listings of important protocol deviations will be provided including the date and relative day in relation to dosing in the relevant period.

## 10.2.2 Reasons Leading to the Exclusion from an Analysis Set

All criteria/reasons leading to the exclusion of a subject from an analysis set will be listed based on the safety set.

Reasons for excluding individual PK concentrations will also be listed separately and flagged in the main listing based on the safety analysis set.

## **11 Demographics and Other Baseline Characteristics**

### **11.1 Demographics**

Summaries will be given for both the safety and the pharmacokinetic set, if different.

Demographic characteristics will be listed by subject and summarized using the following information from the Screening/Baseline Visit CRF pages.

Demographic characteristics:

- Sex: male, female
- Race: Black or African American, American Indian or Alaska Native, Asian, Native Hawaiian or other Pacific Islander, White, Other
- Ethnic origin: Hispanic or Latino , Not Hispanic or Latino
- Age (years): summary statistics
- Height (cm) at Baseline: summary statistics
- Weight (kg) at Baseline: summary statistics
- BMI (kg/m^2) at Baseline: summary statistics

Age will be taken from the eCRF and cannot be derived from the data because only the year of birth is collected in the eCRF.

BMI will be re-derived (ie, not taken directly from the database) according to the following formula:

- BMI (kg/m^2) = weight (kg) / (height (m) \* height (m))

### **11.2 Medical History**

The medical history will be listed by subject including the preferred term and MedDRA system organ class (SOC) body using MedDRA, current version.

### **11.3 Other Baseline Characteristics**

Other baseline characteristics will be listed by subject and summarized using the following information from the Screening/Baseline Visit eCRF pages.

Other baseline characteristics:

- Smoking status
- Alcohol consumption

## **12 Previous or Concomitant Medications/Procedures**

**Previous medications** are medications, other than trial medications and pre-medications for trial drug, which started and stopped before first administration of trial drug.

**Concomitant treatments** are medications, other than trial medications, which are taken by subjects any time on-trial (on or after the first day of trial drug treatment for each subject).

In case the date values will not allow to unequivocally allocating a medication to previous or concomitant medication the medication will be considered as concomitant medication

Any previous and concomitant medication will be encoded with WHO-DD, latest version. Prior and concomitant medications will be listed by subject (all subjects).

The following information will be displayed in a listing: generic or trade name (as reported in eCRF), WHO drug name (including ATC-2nd level and preferred term), dose/unit, route, frequency, reason for use, start/end date and time.

Concomitant procedures will be presented in a data listing.

## **13 Treatment Compliance and Exposure**

A listing of date and time of each drug administration and each blood sampling including time deviations will be provided sorted by subject.

## **14 Efficacy Analyses**

Not applicable.

## **15 Safety Analyses**

The subsections in this section include specifications for summarizing safety endpoints that are common across clinical trials such as adverse events, laboratory tests and vital signs.

Safety data analysis will be conducted on the Safety Analysis Set.

## **15.1 Adverse Events**

The number and percentage of subjects experiencing at least one TEAE will be summarized by treatment as well as the number of events. A TEAE is an AE with onset after start of treatment. Tables by relationship to trial drug and by severity will be generated. AEs will be coded using Medical Dictionary for Regulatory Activities terminology, latest version.

Incomplete TEAE-related dates will be handled as follows:

- In case the onset date is missing completely or missing partially but the onset month and year, or the onset year are equal to the start of trial treatment then the onset date will be replaced by the minimum of start of trial treatment and TEAE resolution date.
- In all other cases the missing onset day or missing onset month will be replaced by 1.
- Incomplete stop dates will be replaced by the last day of the month (if day is missing only), if not resulting in a date later than the date of subject's death. In the latter case, the date of death will be used to impute the incomplete stop date.
- In all other cases the incomplete stop date will not be imputed.

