Healthy males and females (of non-childbearing potential) between 18 and 55 years of age (inclusive) with total body weight between 50 to 100 kg (inclusive) and body mass index (BMI) between 18.5 and 29.9 kg/m² (inclusive) at the time of the Screening examination.

Investigational Medicinal Product: dose/mode of administration/ dosing schedule:

Tepotinib film-coated tablet (Tablet Formulation 2, TF2) containing 500 mg of drug substance, oral administration.

Omeprazole, 40 mg gastro-resistant hard capsule.

Treatment A: A single oral dose of 500 mg tepotinib will be administered on Day 1 together with 240 mL still water at 30 minutes (min) after start of the breakfast which will have to be consumed completely within 25 min.

Treatment B: Single doses of 40 mg omeprazole will be administered in the fasted state in the morning of Days 1 to 5. In the morning of Day 5, also a single oral dose of 500 mg tepotinib will be administered, in **fasted state**, 2 h after the omeprazole administration.

Treatment C: Single doses of 40 mg omeprazole will be administered in the fasted state in the morning of Days 1 to 5. In the morning of Day 5, also a single oral dose of 500 mg tepotinib will be administered in a **fed state**, 2 h after the omeprazole administration and 30 min after start of breakfast.

Reference therapy: dose/mode of administration/dosing schedule: Not applicable

Planned trial and treatment duration per subject:

About 2 months from Screening to End of Trial Visit, treatment on Day 1 of Treatment A and Days 1 to 5 of Treatments B and C.

Statistical methods:

A linear model with TREATMENT, PERIOD, SEQUENCE and SUBJECT (SEQUENCE) as fixed effects will be applied to log-transformed PK parameters C_{max} , AUC_{0-t} , and $AUC_{0-\infty}$ based on the PK analysis set. Treatment differences C-A and C-B on the log scale will be estimated for C_{max} , AUC_{0-t} , and $AUC_{0-\infty}$ together with their 90% confidence intervals (CIs). Point estimates and CIs will be back-transformed to the original scale.

The relative bioavailabilities C/A and C/B will be calculated for each subject.

Summary statistics will be provided for all parameters.

Table 1 Schedule of Assessments - Screening and End of Trial Visit

Assessment / Activity	Screening	End of Trial Visit
Day	-21 to -2	7 (\pm 1) days after last drug administration in the final period
Written informed consent ^a		
Ambulatory visits	X	X
In-/exclusion criteria	X	

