### **15.1.1 All Adverse Events**

All AEs recorded during the course of the trial (ie, assessed from signature of informed consent until the end of the Follow-up/End of Trial visit) will be coded according to MedDRA latest version and assigned to a SOC and PT.

TEAEs will be summarized by worst severity, using MedDRA latest version preferred term as event category and MedDRA primary system organ class (SOC) body term as Body System category. The severity of AEs will be graded using the “National Cancer Institute - Common Terminology Criteria for Adverse Events” (NCI-CTCAE) guideline, as detailed in the study protocol.

TEAEs related to trial treatment are those events with relationship missing, unknown or related.

The following will be summarized in an overview table with the number and percentage of subjects (and the number of events) by treatment and overall:

- Any TEAE
- Any trial treatment related TEAEs
- Any TEAE related to omeprazole
- Any TEAE related to tepotinib
- Any serious TEAEs

- Any trial treatment related serious TEAEs
- Any omeprazol related serious TEAEs
- Any tepotinib related serious TEAEs
- Any severe TEAE (grade  $\geq 3$ )
- Any trial treatment related severe TEAE (grade  $\geq 3$ )
- Any omeprazol related severe TEAE (grade  $\geq 3$ )
- Any tepotinib related severe TEAE (grade  $\geq 3$ )
- Any TEAEs leading to death
- Any trial treatment related TEAEs leading to death
- Any omeprazole related TEAEs leading to death
- Any tepotinib related TEAEs leading to death

TEAEs will be summarized by treatment and overall in tables with:

- The number and percentage of subjects by treatment with at least one TEAE and the number of events overall and by SOC and PT. Group/SOC terms will be sorted alphabetically and PTs within each group/SOC term will be sorted by descending frequency.
- The number and percentage of subjects by treatment with at least one non-serious TEAE and the number of non-serious TEAE applying frequency threshold of 5%. Group/SOC terms will be sorted alphabetically and PTs within each group/SOC term will be sorted by descending frequency.

In addition the following tables will be provided. Group/SOC terms will be sorted alphabetically and PTs within each group/SOC term will be sorted by descending frequency (based on all treatment groups combined):

- A table by severity of TEAEs with the number and percentage of subjects by treatment with at least one TEAE and the number of events by SOC and PT.

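### The adverse event tables have no category for the omeprazole-only days of Treatments B and C, so events there carry a tepotinib label or none

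*SAP*

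**What the plan says.** SAP 9 introduces the column headings with "The following treatment labels will be used in listing and tables". There are three: tepotinib alone fed, "tepotinib + omeprazole, fasted", and the fed counterpart of the latter. There is no heading for omeprazole without tepotinib.

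SAP 15.1 sets the unit of the tables: "The number and percentage of subjects experiencing at least one TEAE will be summarized by treatment as well as the number of events". It defines the events counted: "A TEAE is an AE with onset after start of treatment". It does not say which drug or period starts the clock, when a treatment's window ends, or how an event is assigned to a treatment. Protocol 8.5.4 also says only that the summary is by treatment.

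The Protocol Synopsis says of both B and C: "Single doses of 40 mg omeprazole will be administered in the fasted state in the morning of Days 1 to 5". Tepotinib is given once, on Day 5, two hours after that day's omeprazole (Protocol Table 3, footnote g; Protocol 6.2).

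Three other parts of the SAP bear on the point:

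- SAP 15.1.1 adds causality rows to the overview table, such as "Any TEAE related to omeprazole".
- SAP 15.3 anchors one laboratory shift table on tepotinib: "Discharge versus Pre-dose (Tepotinib administration) within periods".
- SAP 9 places the default baseline before the first drug of each period, which in B and C is omeprazole.

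**The concern.** A secondary objective (Protocol 4.2) is the safety and tolerability of tepotinib alone and with omeprazole. The table that serves it compares A with B and C. If B and C include several days on which only omeprazole was taken, the combination columns mix two exposures and cover more time than the A column.

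With 12 subjects, one subject more or less moves a column percentage by 1/12 = 8.3 points, so a few mild events during the omeprazole run-in could change how the table reads.

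There is also an edge case. The Safety Analysis Set needs only one dose of planned study drug plus one later safety assessment, and it is analysed by treatment actually received. A subject who stopped on Days 1 to 4 of a first-period B or C would be in the set without ever having had tepotinib, and only tepotinib labels would be available.

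**Working it through.** The documents do not state the length of the omeprazole-only phase, so it is derived from the dosing schedule.

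**Inputs.** Omeprazole on the mornings of Days 1 to 5 (Synopsis); tepotinib 2 h after the Day 5 dose (Table 3); last blood sample 144 h after tepotinib (Protocol 7.5.1); 12 subjects, two in each of six sequences (Protocol 8.2); at least 14 days between tepotinib doses (Protocol 5.1); End of Trial Visit 7 ± 1 days after the last tepotinib dose (Protocol 5.1). Assumption: omeprazole is given at the same clock time each morning.

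**Check of the timeline.** With tepotinib on Day 5, 72 h later is Day 8 and 144 h later is Day 11, as in Table 3.

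**Length of the phase.** 4 × 24 h + 2 h = 98 h (97 to 99 h if the clock time shifts by up to 1 h).

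**Scheduled window, first dose to last sample.**
- B or C: 98 + 144 = 242 h.
- A: 144 h.
- Ratio 242/144 = 1.68; omeprazole-only share 98/242 = 40%.

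**Number of phases.** 12 subjects × 2 = 24. Sequences 3 to 6 start with B or C, so 4 × 2 = 8 phases precede any tepotinib. The other 16 follow an earlier tepotinib dose by at least 14 × 24 − 98 = 238 h, about 238/30 = 7.9 of the roughly 30 h half-lives given in Protocol 5.2.2.

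**Where those events go under two possible rules.**

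| Rule | Events in the 24 phases are labelled |
|---|---|
| By regimen (treatment of the current period) | 12 phases to B, 12 to C, 0 to A |
| By last tepotinib dose | 8 to A, 4 to B, 4 to C, 8 to no label |

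For the second row, a B or C period directly follows A in A-B-C, A-C-B, B-A-C and C-A-B (8 phases). C follows B in A-B-C and B-C-A (4). B follows C in A-C-B and C-B-A (4).

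**If regimen windows ran to the next period's first drug.** Take 14 days between tepotinib doses, End of Trial at 7 days and the phase as 4 whole days. In the sequence order of Protocol 8.2:
- A: (10 + 10 + 10 + 7 + 10 + 7)/6 = 9.00 days.
- B: (14 + 11 + 18 + 14 + 11 + 18)/6 = 14.33 days; C has the same mean.
- Ratio 14.33/9.00 = 1.59.
- After removing the omeprazole-only phase: 10.33 against 9.00, ratio 1.15.

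At an assumed 21 days between doses the means are 19.00 and 13.67 days (1.39), or 15.00 against 13.67 (1.10) after removal. Removing the phase therefore brings the windows close to equal length but not fully equal.

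**An equal window.** 0 to 144 h after tepotinib closes before the next period's first drug (238 h at the earliest) and no later than the earliest End of Trial Visit (6 × 24 = 144 h).

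**Imputed onset dates.** For a fully missing onset, or a partial one that matches the month and year, or the year, of treatment start, SAP 15.1 says "the onset date will be replaced by the minimum of start of trial treatment and TEAE resolution date". In sequences 3 to 6 the start of trial treatment is the first omeprazole dose, so this rule can put an event into the omeprazole-only phase. The second rule sets a missing day or month to 1, which can put an onset into any window.

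**The case against.** The strongest reply is that counting by regimen is coherent. B and C are defined as regimens that include five days of omeprazole, omeprazole is itself a study drug, and tolerability of omeprazole alone is not an objective. The default baseline in SAP 9 also precedes the first drug of the period, so change from baseline in laboratory values, vital signs and ECG spans the run-in as well. This stands in part. It shows that regimen-level reporting is the SAP's general convention and that the laboratory shift table is an exception. A reader might infer from the shift table that the SAP separates the run-in elsewhere and merely forgot it for adverse events; the baseline rule does not support that. The convention still leaves a column headed tepotinib plus omeprazole holding events that arose before tepotinib was given.

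A reader might also infer that the tables must be tilted toward more events on the combination. That holds only under regimen-level counting. Under attribution to the last tepotinib dose, A would receive the largest share of the labelled phases (8 of 16). The SAP states neither rule.

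Finally, the causality rows, the dosing listing (SAP 13), the planned time from dosing (SAP 9) and the event listings let a reader place single events, which is practicable with 12 subjects. That is true. However, causality records judgement rather than the drug taken at onset, the SAP does not say which dose the time from dosing refers to, and none of these outputs alters the by-treatment counts.

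**Conclusion.** The concern holds as a gap in attribution with a mislabelled exposure. The three labels cannot describe a planned 98 h phase that occurs 24 times, 8 of them before any tepotinib. Regimen-level counting is the most natural reading and agrees with the per-period baseline. It rests on inference, because the SAP gives no explicit rule. Under it, B and C can gain events that A cannot, over 242 h against 144 h. Under the alternative, the events carry an earlier period's tepotinib label or none. The direction is conditional; the wrong label is not.

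The impact is modest. The tables are descriptive, no hypothesis is tested and the pharmacokinetic analysis is unaffected. The figures above measure scheduled time, not events. The documents give no background rate, and detection on Days 1 to 4 may be lower, since Protocol 7.1.2 lists only omeprazole dosing and a Day 4 physical examination there, although Table 3 shows adverse event monitoring throughout. A claim that the safety comparison will be wrong by some number of subjects has no support.

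**What to change.** In SAP 9 and 15.1:

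1. Add an omeprazole-alone category for onset from the first omeprazole dose of a B or C period to just before tepotinib on Day 5. Count each subject once across the two phases, or show the phases by period.
2. Assign onset from the tepotinib dose to the next period's first drug, or to End of Trial, to A, B or C.
3. Assign Day 5 events without an onset time to B or C and flag them. Flag any event whose onset date is imputed under either rule in SAP 15.1, and do not let the imputation place it in the omeprazole-alone category.
4. Optionally, show onset within 0 to 144 h after tepotinib as the equal-length comparison of A, B and C, with later events beside it.

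The planned overall column keeps every treatment-emergent event.

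The cost is wording in two SAP sections and one derivation from onset and dosing times. The downsides are an extra column that covers only about four days per period and so is not comparable in length with the others, and a flag for missing or imputed onset, since Protocol 7.4.1.2 asks for onset times only where timing relative to dosing matters. The optional step adds a second set of counts.
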